## **VERSION HISTORY**

Version #	Version Date	Summary of Changes
1.0	08DEC2020	Initial protocol
2.0	28 Feb 2021	Protocol amendment submitted to allow screening online.
3.0	08MAR2021	Protocol amendment: response to administrative clarification of request
		to remove Post-exposure prophylaxis and added final factorial design.
3.1	30APR2021	Includes response to FDA questions on full factorial design.
3.2	08July2021	Small updates, mostly around data collection
3.3	02 Sept 2021	Small update around Inclusion criteria
3.4	08 Dec 2021	Updated sample size.

VERSION 3.4

## **ABBREVIATIONS/DEFINITIONS**

- ACE2 Angiotensin-Converting Enzyme
- AE Adverse Events
- AHC-IE Academic Health Center Information Exchange
- ARDS Acute Respiratory Distress Syndrome
- COVID-19 Disease caused by the virus SARS-CoV-2, or "Wuhan coronavirus"
- CLIA Clinical Laboratory Improvement Amendments
- CTSI Clinical and Translational Science Institute
- DM Type 2 Diabetes Mellitus
- DSMB Data Safety Monitoring Board
- ECMO Extracorporeal membrane oxygenation
- eConsent Electronic consent
- ED Emergency Department
- EGFR Estimated Glomerular Filtration Rate
- EHR Electronic Health Record
- ER Extended Release
- GDF 15 Growth/Differentiating Factor 15
- ICF Informed Consent Form
- ICU Intensive care unit
- IDS Investigational Drug Services
- IL-6 Interleukin 6
- IL-10 Interleukin 10
- IQR Interquartile Range
- IR Immediate Release
- MHealth University of Minnesota Health
- mtDNA Mitochondrial DNA
- mTOR Mammalian Target of Rapamycin
- NDMA Nitrosodimethylamine
- NETs Neutrophil-Extracellular Traps
- RC's Research Coordinators, and refers to members of the study team (includes project manager, Co-I, PI).
- SAE Severe Adverse Event
- SARS Severe Acute Respiratory Syndrome
- SOPs Standard Operating Procedures
- SIREN Strategies to Innovate Clinical Trials network
- TLR7 Toll-Like-Receptor 7
- TNF-alpha Tumor Necrosis Factor alpha
- UMMC University of Minnesota Medical Center

# 1.0 Objectives

1.1 Title:

COVID-OUT: Outpatient treatment of SARS-CoV-2 infection, a factorial Randomized Clinical Trial.

Purpose:

- 1) To understand whether metformin vs fluvoxamine vs ivermectin vs metformin+fluvoxamine vs metformin+ivermectin are superior to placebo in nonhospitalized adults with SARS-CoV-2 infection for preventing COVID-19 disease progression.
- 2) To understand if the active treatment arms are superior to placebo in improving viral load, serologic markers associated with Covid-19, and gut microbiome in non-hospitalized adults with SARS-CoV-2 infection.
- 3) To understand if any of the active treatment arms prevent long-covid syndrome, PASC (post-acute sequelae of SARS-CoV-2 infection).

## 2.0 Background

2.1 Significance of Research Question/Purpose:

Severe acute respiratory syndrome coronavirus 2 (SARS-CoV-2) is a rapidly spreading viral infection causing COVID-19 disease. While vaccine development for SARS-CoV-2 has been promising, there may be hurdles to wide distribution, reduced immunity in persons with advanced age or obesity (a state of thymic aging), and reduced willingness among the public to receive a vaccine developed so quickly. Additionally, new strains appear resistant to the vaccines.

2.2 Preliminary Data:

Several observational studies have shown an association with decreased mortality with outpatient metformin use in patients who were then hospitalized with COVID-19, including a study we conducted. Two prospective studies have found efficacy of fluvoxamine in prevention hospitalization and death. Biophysical modeling of the SARS-CoV-2 life cycle, which accurately predicted the efficacy of remdesivir and the lack of efficacy of hydroxychloroquine, identified viral protein translation, which is inhibited by mTOR inhibitors such as metformin, as an especially sensitive node in the model (Castle et al., 2020).

2.3 Existing Literature:

Table 1: Existing Literature	
------------------------------	--

Papers in 20	20 with observatio	nal mortality findings re	elated to metformin and COVID-19.
Author	Population	Methods	Finding
Luo et al. 	283 adults with	Retrospective review,	Hospital mortality 2.9% in metformin
Am J Trop	DM hospitalized	appears to be of home	group vs 12.3% in no-metformin group,
Med Hyg	with COVID-19	metformin us; 104 in	p=0.01. OR for survival: 4.36 (1.22-
	in Wuhan.	metformin, 179 in no-	15.59, p=0.02). No difference in length of
		metformin group	stay. No mortality difference based on use
			of other DM medications.

Cariou et	1,317 adults	Multi-cente	r	HbA1C was	not associated with	main	
$al^2$	with DM in	observation	al study.	outcome $(p=0.28)$ or death $(p=0.91)$ ;			
"Coronado	France, with or	Main outcome:		home metformin was associated with			
study"	without home	mortality or		lower mortality OR 0.59 (0.42, 0.84).			
Diabetalgia	metformin use	intubation;	Secondary	Increased ri	sk of death with insu	lin OR	
		outcome wa	IS	1.71, (1.20,	2.43). No association	n with	
		mortality.		other DM m	neds.		
Bramante	6,256 adults	Retrospectiv	ve review	Metformin	was associated with a	reduced	
et al.	with DM or	of USA UH	G claims	mortality in	females: OR 0.759 (	0.601,	
Lancet	obesity	data of hom	e		copensity matching;		
Healthy	hospitalized for	metformin use (claims		(0.631, 0.96	5) by a mixed effects	s model;	
Longevity.	COVID-19 in	for $\geq 90$ days in prior		· · · · · · · · · · · · · · · · · · ·	OR 0.785 (0.650, 0.951) by Cox		
	the US.	12 months)		proportional-hazards.			
Crouse et	239 persons with	Retrospective review		- Metformin treatment was independently			
al.	diabetes and	,	of 25,326 subjects		associated with a significant mortality		
Metrxiv.org	COVID-19	tested for C			subjects with diabet		
		between 2/2	-	COVID-19,	OR 0.33 (0.13-0.84;	p=0.02)	
		6/22/20 at U					
					users with COVID-		
Chen et al. 	904 patients with	Retrospectiv		Metformin users had lower IL-6 (4.07 vs			
Diabetes	COVID-19, 136	of patients v		11.1, p=0.02). In PCR-confirmed cases,			
Care	of whom had	and COVID	-	IL-6 was also lower in metformin users			
	DM	association			etformin users (4.77		
		glucose low	0		o differences betwee		
		medications			n-users. GLP-1 use no	ot	
D	0.105	T 1		reported.		DICI	
Bramante	2,135 patients	Lab	No Metfor		Metformin	P Value	
et al, under	with SARS Co-	Bicarb	25(8), n=4		26(5), n=25	0.38	
review.	V-2, subset with	Lactate	1.5 (1.1), n		1.3 (0.5), n=7	0.78	
	lab values	IL-6	1,702 (1,01	//	54 (69), n=7	0.08	
		CRP	111 (83), n	=290	84 (75), n=16	0.02	

[figure not shown]

Figure 1: Pooled risk of mortality in hospitalized COVID-19 patients with diabetes with preadmission metformin. (heterogeneity: I2=29%; p=.23).

Prior to COVID-19, the exact mechanisms by which metformin conveyed benefit was a matter of debate. There are several ways by which metformin may offer protection from SARS-CoV2.

## Existing Literature on Mechanistic Reasons for Metformin to be Effective against COVID:

[figure not shown]
High glucose is associated with worse COVID-19 outcomes: Metformin reduces blood glucose levels, but not below physiologic levels, by reducing hepatic gluconeogenesis. Worse glucose control has also been associated with higher mortality and end-organ complications in patients with COVID-19.

Metformin could decrease endothelial injury and its complications: Metformin has been shown to improve microvascular endothelial function in women perhaps due to a significant increase in response to acetylcholine, decrease in insulin resistance, and non-significant decrease in tissue plasminogen activating factor, as was shown in a randomized control study of 8 weeks of metformin versus placebo in women with angina and normal coronary arteries . Pulmonary vascular endotheliatis has been observed in the lungs of patients with COVID-19. Endothelial dysfunction may be an important mechanism and therapeutic target in mitigating COVID-19 sequelae. Metformin decreases thrombosis in long-term follow-up, possibly by inhibiting platelet activation factor and mitochondrial DNA (mtDNA) release, and may mediate improved cardiovascular outcomes via mechanisms beyond glucose control. COVID associated coagulopathy and thrombosis is a unique attribute to this disease, and the pathophysiology is poorly understood. Further, frequently widespread micro and macrovascular thrombosis has been reported in autopsies of patients with COVID 19.

Metformin decreases neutrophil-extracellular traps (NETs), and the neutrophil to lymphocyte ratio. NETs are microbiocidal compounds containing DNA, histones, and proteins. Sera from patients with COVID-19 demonstrate elevated levels of these histones and DNA components. It has been hypothesized that excessive NET formation leads to cytokine storm and microthrombus (possibly independent of tissue factor), and ultimately acute respiratory distress syndrome (ARDS) in COVID-19. Lymphopenia and neutrophil infiltration in pulmonary capillaries have been an important feature of severe COVID-19 disease. Metformin's inhibition of NET release could therefore mitigate the development of downstream lung injury.

Metformin could decrease the viral cycle: There is evidence that metformin increases endosomal pH via action on vacuolar ATPase and/or endosomal Na+/H+ exchangers, thus reducing viral replication. Metformin leads indirectly to alteration of the mammalian target of rapamycin (mTOR) pathway, which could decrease the viral lifecycle through effects on proteins including Orf9c and Nsp7. Biophysical modeling of the SARS-CoV-2 life cycle, which accurately predicted the efficacy of remdesivir and the lack of efficacy of hydroxychloroquine, identified viral protein translation, which is inhibited by mTOR inhibitors such as metformin, as an especially sensitive node in the model. Metformin has been shown to inhibit mTOR, and mTOR inhibition is associated with efficacy against MERS and COVID-19.

#### VERSION 3.4

Metformin may decrease entry of SARS-CoV-2 into cells: Activation of AMPK by metformin increases expression of angiotensin-converting enzyme 2 (ACE2). Simultaneously, increased phosphorylation of the ACE2 receptor leads to conformational changes that could theoretically decrease SARS-CoV-2 binding and entry into cells.

[figure not shown]

Figure 4, Karam et al, in press.

Metformin has immune-modulatory effects: In patients with and without diabetes, metformin has been shown to favorably alter inflammatory mediators, including interleukin 6 (IL-6), TNF-alpha, and to possibly boost interleukin 10 (IL-10), and suppress the C-C motif chemokine ligand. Metformin's activation of the AMPK/mTor/Stat3 pathway seems to steer

VERSION 3.4

macrophages away from the pro-inflammatory classical activation that produces TNF/IL6/IL1b, cytokines that contribute to morbidity in COVID-19. Possible evidence of this effect was seen in a retrospective study by Chen et al of, review 904 patients with COVID-19 which showed that metformin users had lower IL-6 levels compared to non-metformin users (Table 2). Metformin also inhibits toll-like-receptor 7 (TLR7) signaling and interferon production, which appears important to COVID-19 pathophysiology. Metformin also inhibits IgE- and aryl hydrocarbon-mediated mast cell activation. Mast cell activation has been implicated as an early indicator of inflammatory response to SARS-CoV-2. and possibly an indicator of impending cytokine storm. Mast cells from female rats have been found to cause a greater increase in tumor necrosis factor alpha (TNF-alpha) than mast cells in male rats, which may explain the observational findings of reduced mortality in women on metformin, but no among men on metformin.

Metformin has a history of anti-infectious properties: Metformin was found to have antiviral activity before SARS-CoV-2. In the 1940s and 1950s, metformin was used against influenza (as "Flunamine"), and was found to be effective against parainfluenza and cowpox. Metformin has also been associated with improved response to anti-infectious agents in HIV and tuberculosis. With the Zika virus, another RNA virus, activation of AMPK by metformin resulted in restricted viral replication by potentiating innate antiviral responses and decreasing glycolysis, with PKA Inhibitor PKI leading to decreased viral infection and replication. In patients with hepatitis C, metformin has been associated with improved virologic response to antivirals through decreased insulin resistance.

[figure not shown]
Metformin's past anti-infectious benefits have been both against the infectious agent directly, as well as by improving the underlying health of the human host. It is unknown if the lower mortality observed in patients infected with COVID-19 who are on metformin is due to direct activity against the virus itself, improved host substrate, or both.

## Fluvoxamine

In addition to metformin, fluvoxamine appears to have important anti-viral and antiinflammatory effects in SARS-CoV-2 infection. There is evidence that SARS-CoV-2 infection causes ER stress and activates pathways of unfolded protein response. This response is related to several signaling pathways such as autophagy, apoptosis, innate immunity, proinflammatory response, and MAP kinase pathways. Further study has demonstrated that the virus can take over the ER by utilizing the stress sensor inositol requiring enzyme 1 (IRE1) which helps to regulate coronavirus-induced autophagy. This ER response provides a potential pathway for immunomodulatory treatment.

Sigma-1 receptor (S1R) is an ER chaperone protein that regulates cytokine production through interaction with IRE1. S1R modulation has demonstrated significant changes to coronavirus replication, and atypical antipsychotics with S1R activity have displayed protective effects against clinical deterioration. Fluvoxamine is a selective serotonin reuptake inhibitor that is a powerful S1R agonist. Fluvoxamine has previously been shown to protect mice from septic shock and reduce the inflammatory response. There is potential for fluvoxamine as an immunomodulatory treatment for SARS-Cov-2. Fluvoxamine in CACO2 cells infected with

SARS-Cov-2 had a reduction in production of a subset of cytokines including IL-6, IL-8, CXCL1, and CXCL10. A randomized controlled clinical trial of 152 patients showed that patients who received fluvoxamine were less likely to experience clinical deterioration, or serious adverse events due to SARS-Cov-2 when compared to placebo (0% vs. 8%). A follow up real world observational cohort had similar findings of 0% (0/65) hospitalization with fluvoxamine vs. 12% (6/48) with observation.

## Ivermectin

Ivermectin has also shown anti-inflammatory effects that would reduce the harmful cytokine cascade noted in severe Covid-19 disease. A recent trial assessing a multi-therapy including 12mg one-time dose of ivermectin found a 75% reduction in hospitalizations. Another small double-blinded RCT showed significant increased chance of viral clearance after a 5-day course of ivermectin. Another March 2021 RCT reported no effect on diminishing symptoms, but was under-powered for assessing reductions in hospitalization. An RCT with ivermectin must be done in the US, as endemic strongyloidiasis in other countries may confound results.

#### Importance of factorial design approach:

It is important to study all 3 of these medications in a factorial design because they all fit into the same implementation category: all are existing, FDA-approved, generic, inexpensive, currently available world-wide, and have long records of excellent safety. They each hold few medication or co-morbidity related contraindications, and none of them require any follow-up for short-term use.

A factorial design approach is important for minimizing the percentage of patients who receive placebo in this urgent public health emergency. A factorial design allows us to efficiently compare the drugs directly to each other, as well as combination arms, while maintaining a placebo control. While EUA's and prospective cohorts have become common in the body of literature about Covid-19, we feel that randomized placebo control is necessary for best understanding medication effect.

## 3.0 Study Endpoints

3.1 Primary Endpoint:

1) Clinical progression, defined as: Emergency department visit for any COVID-19 related symptom (including hospitalization or death) or decrease in O2 saturation ( $\leq 93\%^{*59}$  on room air, or need for supplemental oxygen to maintain an O2 saturation >93%) by 14 days.

\*COVID-19-related symptoms as defined by the CDC\*, or attributed to COVID by treating team. \*https://www.cdc.gov/coronavirus/2019-ncov/symptoms-testing/symptoms.html. Currently those symptoms include: Fever or chills, cough, shortness of breath or difficulty breathing, fatigue, muscle or body aches, headache, new loss of taste or smell, sore throat, congestion or running nose, nausea or vomiting, or diarrhea.

Secondary Endpoints:

- Clinical deterioration on a Likert-type scale: (0) No symptoms (1) moderate severity of illness as defined by O2 saturation ≤93% but no supplemental oxygen requirement; (2) O2 saturation >93% plus supplemental oxygen requirement; (3) ED visit for any COVID symptoms (4) hospitalization for any COVID symptom; (5) the above, plus ventilator support requirement; (6) the above, plus ventilator support for at least 3 days; (7) death; and by number of days requiring supplemental oxygen; hospitalization; ventilator support), by Day 28. Hospitalized patients may be followed for maximal outcome.
- Time to meaningful recovery (symptoms or severity improved by one category and sustained for at least 36 hours)
- Maximum symptom severity experienced by Days 14, 28 (Appendix B)
- Incidence of all-cause study medicine discontinuation (Day 14).
- Portion of participants with Post-Acute Sequelae of SARS-CoV-2 Infection (PASC)
- a. PASC assessment monthly after enrollment for 6 months to 12 months with the "Questionnaire to characterize long COVID." (Appendix G).
- •

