#### 5.4.3 Lab Collection:

Labs will be considered optional if patients want to participate but not collect the nasal swab and/or stool. For interested and willing patients, labs will be done on approximately Day 1, 5, and 10.

The SARS-CoV-2 PCR may be assessed via self-collect anterior nasal swab, which may be done over phone or video with the RC if the patient prefers this aid. Detailed instructions for the patient are in Appendix B, the patient manual.\*

The GFR blood tests may be collected by the clinic, mobile phlebotomy, or finger-prick, with the option of it being done while on secure video or phone with the RC if the patient prefers this aid. Blood will be collected in a microtainer tube and placed in approved shipping materials that will then be returned to the lab via courier or mail.

Stool sample collection is optional and would be done with a self-collect microbiome kit. Patients will be given detailed lab collection procedures for each test.

Missing biospecimens will not constitute protocol deviations.

5.4.4 Seeking Medical Care:

Patients will be advised to seek medical care, as they would if they were not in the study, including other treatments of Covid-19. Participants will be advised that the distribution of home oxygen monitors is not meant to prevent them from seeking medical care, and that they should seek medical care as they would whether they were in the study or not.

5.5 Follow-up Procedures:

CONFIDENTIAL

Data on clinical progression may be collected on any consented patient by EHR review, from contact if patient not available, by patient self-report (phone, survey, email, text), or by vital records search.

RC's may contact patients on Day 2 to assess side effects or questions. If patients experience side effects that they find distressing, the RC's will discuss approaches to minimize side effects (See Section 4.6 Dose Modification), and to advise the patients that side effects usually subside after about 5 days.

Participants will be asked to track symptoms (including temperature and oxygen saturation), and medication adherence daily. Patients will receive a thermometer and oxygen saturation monitor with their study drug (details below). Study personnel will attempt to contact with patients about every 2 to 3 days during the 14-day intervention window to review study drug adherence, and review symptoms for possible adverse events.

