#### 5.5.1 Survey Data Collection:

Participants will be given a hard-copy symptom log to capture COVID-19 related symptoms daily (Appendix B). Patients will be asked to record their medication adherence, their temperature, and their oxygen saturation with a home O2 monitor every day for the 14 days of participation.

The symptom log may also be available by Part-11 approved means (such as via text or app). For patients not using app, RC's will assess whether the symptom logs are being filed out daily at each contact point with patients. Adherence with taking the medication will be assessed via self-report daily in the log or software to record adherence.

Survey questions will be listed in a physical paper study log that is included in the study box that is sent to patients. Patients can fill out the survey on these paper logs and then send a picture of the logs to study staff (no identifying information on the pages of the logs); patients can also receive the survey questions via Part 11-certified electronic means; or patients can report the survey question answers to the RC over the phone if they prefer.

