## Day 28 Contact:

- Symptom log (adapted from FDA suggestions, Appendix B)
- Assess clinical progression (Query for hospitalization or ER visit or SAEs that occurred between Day 14 and Day 28)
- Assess other medicines used during study period

A vital status search will be conducted on all randomized patients.

Days are +/- 3 days, for the first 14 days every attempt will be made to capture data +/- 1 day.

Patients will be advised to seek medical care for symptoms in the same way that they would if they were not in the study.

Participants will be reimbursed for their time via a trackable means (i.e. Clin card or Visa card), after completion of these study activities: enrollment; Day 1 labs; Day 5 labs; Day 10 labs; Day 14 log returned; and Day 28 follow-up.

Monthly Contact: Patients will be assessed approximately once/month for 9 months after the completion of their Day 28 contact to assess for ongoing symptoms suggestive of post-acute sequelae of COVID-19. Patients will receive reimbursement for each of these monthly follow-ups completed.

5.6 Study Duration:

14 days of treatment with follow-up, and a follow-up survey at 28 days then monthly for 9 months.

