## Schedule of Assessments:

Symptoms: Days 1- 14, 28. Side effects: Day 2 AE's/SAE's: Days 2, 5, 10, 14, 28 Clinical Progression: Days 5, 10, 14, 28 PASC: Monthly after Day 28

5.7 Retention:

We will make every effort to keep participants engaged through the entirety of the study so as to minimize missing data (for example regular calls, texts, emails, assessment via vital records search, and contact with family members if needed). The principal investigators have recent experience working with patients on COVID-19 trials, and they will leverage this experience.

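### Maximum symptom severity by Day 28 is not supported by the stated schedule, which has no symptom entry on Days 15 to 27

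*Protocol*

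**What the plan says.** **Endpoints.** Protocol section 3.1 includes among the secondary endpoints "Maximum symptom severity experienced by Days 14, 28 (Appendix B"). It also includes time to meaningful recovery, defined as "symptoms or severity improved by one category and sustained for at least 36 hours", with no time horizon stated.

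**Collection.** Section 5.5.1 describes the instrument: "Participants will be given a hard-copy symptom log to capture COVID-19 related symptoms daily (Appendix B"). The day-by-day timeline in section 5.5.2 lists the log on each of Days 1 to 14 and next at the Day 28 contact, as "Symptom log (adapted from FDA suggestions, Appendix B"). The Schedule of Assessments agrees: "Symptoms: Days 1- 14, 28".

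**Other contacts.** Section 5.5 has staff review symptoms within the treatment period only: "Study personnel will attempt to contact with patients about every 2 to 3 days during the 14-day intervention window". The Day 28 contact carries a separate item, "Assess clinical progression (Query for hospitalization or ER visit or SAEs that occurred between Day 14 and Day 28"). Long-COVID questionnaires are roughly monthly. Section 5.5 counts them from the end of the 14-day treatment period and section 5.5.2 from the Day 28 contact.

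**The concern.** A maximum experienced by Day 28 needs severity information on the whole of Days 1 to 28. The protocol schedules it for the first fourteen days and for the last one. What the Day 28 maximum can add to the Day 14 maximum is a worse symptom day after the treatment course ends, and that is the period with almost no symptom data.

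Two consequences follow if nothing else is collected. The recorded Day 28 maximum is biased in one direction, downwards, for any participant whose worst day falls between Day 15 and Day 27. And the Day 14 and Day 28 results will agree largely by construction, so that agreement could be misread as evidence that a difference seen at Day 14 persisted to Day 28.

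This is not a gap that the SAP can close. The SAP can choose a model or a censoring rule, but it cannot supply symptom data for days on which none are scheduled. The endpoint and the schedule are both fixed in the protocol.

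**Working it through.** The plan gives no figure on this point to reproduce. The check is a count of scheduled symptom entries against the window of the endpoint.

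**Inputs**
- Endpoint windows: Days 1-14 and Days 1-28 (section 3.1).
- Scheduled symptom entries: each of Days 1-14, and Day 28 (section 5.5.2; Schedule of Assessments).
- Visit windows: 3 days either side, with an effort to stay within 1 day in the first 14 days (section 5.5.2).
- Persistence required for recovery: 36 hours (section 3.1).

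**Coverage**
- Days with an entry: 14 + 1 = 15 of 28.
- Days without: 28 − 15 = 13 (Days 15 to 27); 13/28 = 46%.
- Within Days 15-28: 1 of 14 days has an entry.

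**Do the visit windows close the gap?**
- Day 14 entry 1 day late (Day 15) and Day 28 entry 3 days early (Day 25): Days 16-24 are empty, 24 − 15 = 9 days.
- Day 14 entry 3 days late (Day 17) and Day 28 entry 3 days early (Day 25): Days 18-24 are empty, 24 − 17 = 7 days.
- So the gap narrows at most to a week and does not close.

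**What the recorded maximum is.** Let S(d) be symptom severity on day d.
- Day 14 maximum: M14 = max of S(1), …, S(14). All terms are scheduled.
- True Day 28 maximum: M28 = max of S(1), …, S(28).
- Recorded Day 28 maximum, if the Day 28 entry describes that day: R28 = max of M14 and S(28).
- R28 is taken over a subset of the terms in M28, so R28 ≤ M28 always. R28 falls short exactly when the worst of Days 15-27 exceeds both M14 and S(28). R28 differs from M14 only when S(28) exceeds M14.

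**Does another source fill Days 15-27?**
- Staff symptom review is confined to the 14-day window (section 5.5).
- The Day 28 look-back names hospitalization, ER visits and SAEs, not symptom severity (section 5.5.2).
- The long-COVID questionnaires begin about a month after Day 14 on one statement and after Day 28 on the other. Neither falls within Days 15-27.

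**Recovery.** From the Day 14 entry to the Day 28 entry is 14 × 24 = 336 hours, against a criterion of 36 hours. An improvement first seen on Day 28 began at an unknown point in that interval, and one entry cannot show that it lasted. With entries about 24 hours apart, an improvement first logged on Day 13 is followed by one more daily entry only, which is also short of 36 hours.

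**The case against.** **The Day 28 form is not visible.** The endpoint points to Appendix B, and so does the Day 28 log. Appendix B is not available here, and section 5.6 calls Day 28 a follow-up survey. If the form asks for worst severity since the last contact, the Day 28 maximum is obtainable by recall. The look-back wording belongs to the separate clinical-progression item, so it does not prove that the symptom log lacks a recall period. This stands. A reader might infer that the endpoint cannot be derived at all; the documents do not support that. What they support is that the protocol text states no symptom recall period, describes the log as daily, and states a look-back only for clinical events.

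**Late worsening is not generally missed.** A reader might infer that deterioration after Day 14 goes almost entirely unrecorded. It does not. ED visits, hospitalizations and SAEs are queried at Day 28, section 5.5 adds an EHR search, and section 5.5.2 adds a vital status search. Only worsening that leads to none of these is exposed. Home oximetry readings are a partial exception, since participants record "oxygen saturation with a home O2 monitor every day for the 14 days of participation".

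**Recovery is not contradicted.** Section 3.1 ties only maximum severity to Appendix B, and the recovery definition refers to symptoms or severity, part of which can come from records. No horizon is stated, so the endpoint remains derivable to Day 14 with ordinary right-censoring. The protocol names Kaplan-Meier, log-rank and Cox methods for time-to-event outcomes and leaves details to the SAP. A curve that is flat and then steps at Day 28 would arise only if Day 28 were entered as the event time, which the protocol does not say. This also stands, so recovery is a secondary remark here.

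**The size of the bias is unknown.** A reader might turn the calendar count into a proportion of late peaks missed. That would require late peaks to be equally likely on each day, for which the documents give no basis. Late peaks may be few, since symptom onset more than 7 days before randomization is an exclusion. The log schedule is the same in all arms and the trial is blinded, and no effect on a treatment comparison has been shown.

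**Conclusion.** The point holds for the Day 28 half of one secondary endpoint. On the stated schedule, 13 of 28 days (46%) have no symptom entry, and at least 7 consecutive days stay empty even with the visit windows fully used. The Day 28 maximum is then the Day 14 maximum plus one entry, and it can only equal or understate the true value.

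This rests on one assumption: that the Day 28 log records symptoms on that day, as its description as a daily log implies. If Appendix B already asks for worst severity since Day 14, the main point is answered and the protocol need only say so.

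The count measures coverage, not bias. How many participants have a worse day between Day 15 and Day 27, and whether that differs by arm, cannot be read from the documents.

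For symptom-based recovery, an event first seen on Day 28 can be neither dated within the gap nor shown to have persisted. This needs a rule, but it does not make the endpoint invalid.

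Not affected: the primary endpoint (by 14 days), maximum symptom severity by Day 14, and ED, hospital, SAE and death outcomes to Day 28.

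**What to change.** Choose one of the following for the maximum.

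1. Add one item to the existing Day 28 log asking for the worst symptom severity since Day 14, and state the recall period in section 3.1 and in the Schedule of Assessments. Cost: one question at a contact that already takes place. Downside: a two-week recall, combined with daily records for the first fourteen days, so the two halves of the maximum are not measured in the same way.
2. Define maximum symptom severity over Days 1-14 only, and report Day 28 as symptom severity on that day. Cost: endpoint wording. Downside: the Day 28 maximum is given up.

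If Appendix B already contains the recall item, a sentence in section 3.1 saying so is enough.

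For symptom-based time to meaningful recovery, either censor at the end of daily logging or treat recoveries first seen on Day 28 as interval-censored between Day 14 and Day 28. State also how an improvement first logged too late in the daily period to show 36 hours is handled. This rule may be left to the SAP and costs only wording.
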